9.3.2 Analysis of the Secondary Endpoints

The following incidents by subjects will be summarized: Incidence of Surgical Site Occurrences requiring procedural intervention (SSOPI), incidents of Surgical Site Occurrences (SSOs) (seroma, abscess, dehiscence, hematoma, wound necrosis, ileus, fistula, delayed wound healing), incidence of Surgical Site Infections (SSIs), incidence of self-reported recurrence (i.e., bulge), reoperation requirement of the primary hernia repair to date, including not previously reported in GENVIH-002 study. The proportion of subjects with the incidents will be presented.

9.3.3 Analysis of Device Deficiency

Device deficiencies will be presented by the nature of the device deficiency (e.g. mechanical failure, shunt pathway obstruction, etc.). Each device deficiency will be summarized on a patient basis by tabulating the counts and percentages of subjects with the deficiency. For the patient-based results, a deficiency which occurred multiple times for the same patient will only be counted once. Device deficiency will also be presented on a deficiency basis, where the number of occurrences of each deficiency will be presented. The analysis of device deficiencies will be performed in the enrolled population. By subject listings will be provided for each subject reported.

9.3.4 Analysis of Adverse Events

The incidence rate of each of the adverse device effects from the follow-up visit will be presented. The incidence of adverse events and serious adverse events will be tabulated (frequencies and percentage of patients) by severity and relationship to device and procedure. The analysis of safety will be performed in the enrolled population.

Descriptive statistics will be provided for safety endpoints by surgical procedure. All safety summaries will be presented for the full analysis population. Adverse Device Events will be coded according to Medical Dictionary for Regulatory Activities (MedDRA) AE coding dictionary. All ADEs will be listed. A summary of the frequency count and percentage of subjects reporting each ADE category will be produced for all reported ADEs and SADEs. Relationship of AE verbatim text to group terms and body systems will also be reported. A listing of withdrawals due to ADEs will be provided. Deaths and SADEs will be listed should they occur.

AE listing includes Onset Date, AE Term, Relation to Device, Relation to Procedure, Pattern, Seriousness (SAE), Severity, Treatment, Medication, Surgical, Outcome, End Date. By subject listings will be provided for each subject reported.

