2.2.5 Device Traceability

No device traceability will be performed for the purposes of this study given the study is noninterventional.

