5.5 Strategies for Recruitment

A one-off subject phone (call) visit will constitute the source of data and will be collected using a study-specific eCRF delivered via a phone script by the site responsible or their designee(s). Each patient should be included in the study only once. Patient screening will rely on site identification and contact of prior T-GENVIH-002 study subjects (Sponsor remains blinded) and e-consent process. In these cases, every effort should be made to identify every possible eligible patient. For those that are lost to follow up, site may work directly with a Sponsor approved people search service (Sponsor remains blinded). In order to be eligible for the study, patients should meet all of the eligibility criteria.

For subjects who decline an electronic consent collected remotely, an in-office interview and assistance with completing the electronic consent in person with the site study coordinator or their designee(s) will be offered for the convenience of the subjects and to maximize data collection efforts.

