6.1 Schedule of Data Collection

6.1.1 Eligibility/Consent

- The procedures to be completed are:

- ✓ Identification of the full consecutive series of patients who underwent abdominal wall reconstruction for a minimally invasive surgical approach (i.e., laparoscopic or robotic) hernia with Integra® Gentrix® Surgical Matrix from the prior T-GENVIH-002 study and informed consent for those who volunteer to participate.
- ✓ Creation on the CRF of a new case book for each eligible subject. Each created case book assigns the eligible subject with a study number.
- ✓ Completion of Worksheets/ CRFs: Site will transcribe/transmit the below-mentioned patients' data in study CRFs. The patients' data will originate from a direct interview with the subject by the study coordinator.
- The patients' data to be collected are:
 - ✓ Eligibility:
 - Inclusion Criteria: Ensure the subject meets all the inclusion criteria.

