6.1.2 Visit 1 Questionnaire

The patients' data to be collected from the last data collection of GENVIH-002 study to date, including not previously reported, are:

- Clinically confirmed recurrence of the primary hernia repair
- Self-reported recurrence (i.e., bulge) of the primary hernia
- Surgical Site Occurrences requiring Procedural Intervention (SSOPI)
- Surgical Site Occurrences (SSOs)
- Surgical Site Infections (SSIs)

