9.2.5 Surgery Evaluation

Not applicable.

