9.3 Endpoint Analysis

Primary, Secondary and Safety Endpoints will be analyzed based on the Visit 1 Questionnaire report.

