10. SUBGROUP ANALYSIS

Subgroup analyses may be performed, in which the analysis of endpoints will be presented within subgroups based surgical approach and type of the Gentrax Surgical Matrix Used.

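### The primary recurrence proportion carries no follow-up time, because the SAP names no source for index-surgery date, approach or matrix type

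*SAP*

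**What the plan says.** **Outputs that depend on the index operation.** SAP 9.3.4 states that "Descriptive statistics will be provided for safety endpoints by surgical procedure". SAP 9.2.8 promises a Kaplan-Meier curve of time to recurrence, worded as being for the subjects who had a recurrence. SAP 9.2.9 will summarise complications from the index operation onward. SAP 10 allows, as an option, analysis of the endpoints "within subgroups based surgical approach and type of the Gentrax Surgical Matrix Used".

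**Where the data come from.** SAP 9.2.5, Surgery Evaluation, reads in full "Not applicable". Protocol 5.5 says "A one-off subject phone (call) visit will constitute the source of data", and Protocol 6.1.1 says the patients' "data will originate from a direct interview with the subject by the study coordinator". SAP 9.3 adds that "Primary, Secondary and Safety Endpoints will be analyzed based on the Visit 1 Questionnaire report". Protocol 6.1.2 describes the questionnaire data as "to be collected from the last data collection of GENVIH-002 study to date, including not previously reported" and lists confirmed recurrence, self-reported recurrence, SSOPI, SSO and SSI. Index approach, matrix configuration and surgery date are not on that list. SAP 9.2.2 to 9.2.4 draw demographics, medical history and medication from T-GENVIH-002.

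**The primary analysis.** SAP 9.3.1 reports the proportion of subjects with a clinically confirmed recurrence to date. The primary objective in the Protocol synopsis is continued performance over the longer term.

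**The concern.** This is a long-term follow-up study, so a recurrence proportion has meaning only beside the length of time over which recurrences could have occurred. Subjects had their operations before this study and are contacted once, so time since implantation presumably differs between them. The plan reports the proportion, but no section commits to reporting the time behind it.

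The cause is a gap in the list of imported data. The SAP says so where it takes data from T-GENVIH-002, in three consecutive sections. The next section is where the operation would belong, and it is set aside. Surgery date, approach and matrix type are therefore needed by several outputs and given a source by none. If the plan is followed as written, the reader of the report cannot tell whether a given recurrence proportion reflects short or long follow-up.

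**Working it through.** The planned sample size of about 21 has no formula behind it (SAP 8 says it is not based on hypothesis testing), so there is no figure in the plan to reproduce. The check traces each output to a named source and then illustrates the size of the consequence.

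**Step 1. Trace outputs to sources.**

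| Output | Status | Index-surgery item needed | Source named |
|---|---|---|---|
| Primary proportion, SAP 9.3.1 | firm | surgery date, to interpret it | none |
| Time to recurrence, SAP 9.2.8 | firm | surgery date as time origin | none; origin not defined |
| Index-surgery complications, SAP 9.2.9 | firm | operative record | none; sits badly with 9.2.5 |
| Safety by procedure, SAP 9.3.4 | firm | approach | none; eligibility confirms only laparoscopic or robotic combined (Protocol 5.1) |
| Subgroups, SAP 10 | optional | approach, matrix type | none |

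**Step 2. Look for follow-up time in any planned output.** SAP 9.3.1 gives a proportion only. SAP 9.3.4 lists onset and end dates, but only for adverse events. SAP 9.2.8 is the only time-based analysis and is worded for subjects with recurrences. Taken literally, every subject in that curve has the event, so the curve must fall to zero, and recurrence-free subjects contribute no censored times. With 2 recurrences among 21, the curve would describe 2 subjects and leave out 21 − 2 = 19. The start of the observation window is also stated in two ways: the Protocol synopsis and SAP 5 start at the day of the operation, while Protocol 6.1.2 starts at the last T-GENVIH-002 data collection.

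**Step 3. Illustrate what the missing time conceals.** Assumptions: 21 subjects analysed, 2 recurrences, a constant hazard, and the same follow-up t for everyone. The event count and both values of t are chosen for illustration and are not in the documents.

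- Proportion: 2/21 = 9.5%.
- Cumulative hazard: −ln(1 − 2/21) = −ln(19/21) = 0.100.
- t = 2 years: 0.100/2 = 0.050, about 5.0% per year.
- t = 5 years: 0.100/5 = 0.020, about 2.0% per year.

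The planned output is 9.5% in both cases. The ratio of 2.5 is simply 5/2; it shows how the answer scales with follow-up and does not estimate anything in this trial.

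**Step 4. What a follow-up summary would not cure.** The exact (Clopper-Pearson) 95% interval for 2/21 is 1.2% to 30.4%. Reporting follow-up makes the proportion interpretable but not more precise.

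**The case against.** The strongest reply is that this is a clarification, not a defect. The population is defined by surgical approach in T-GENVIH-002, the site was chosen for having taken part in that study (Protocol 5.3), and reporting its demographics and history for these subjects already presupposes a link. The parent study probably holds the surgical fields. SAP 9.2.5 heads a descriptive section in a study that performs no surgery, so its entry may mean only that no surgery table is planned. The study is descriptive with no hypothesis, and the subgroups are optional.

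Most of that stands, and it rules out several stronger readings:

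- A reader might infer from Protocol 5.5 and 6.1.1 that the interview is the only data source. SAP 9.2.2 to 9.2.4 show otherwise, since three domains come from T-GENVIH-002.
- A reader might infer that the by-procedure table and the subgroups cannot be produced, or would rest on patients recalling their implant. No section plans to ask patients this, and the documents do not show that the fields are missing from the parent study. What is missing is a named source.
- A reader might take the new study number in Protocol 6.1.1 to mean that the records cannot be linked. The documents are silent on whether the earlier number is kept, and the CRFs are not available to check.
- A reader might conclude from "No device traceability will be performed for the purposes of this study given the study is noninterventional" in Protocol 2.2.5 that a deficiency or explant could not be tied to a configuration. Protocol 7.3.2 asks the site to try to keep the device and packaging for return and provides for root-cause investigation, so this point does not require amending 2.2.5.
- A reader might want a figure for the effect of placing one subject in the wrong group. No split by approach or matrix is given, and the effect depends on whether that subject had an event, so no such figure is supportable.

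The reply does not answer the point about the primary endpoint. Even if the parent study holds every date, no planned output uses them for subjects who remain recurrence-free.

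**Conclusion.** The concern holds in a limited form. The SAP firmly commits to outputs in 9.2.8, 9.2.9 and 9.3.4 that depend on index-surgery facts, sets Surgery Evaluation aside in 9.2.5, and omits those facts from its stated imports. The consequence that matters is that the primary proportion to date is reported without follow-up time and no planned output gives time since implantation for recurrence-free subjects, so performance over the longer term cannot be interpreted. In the illustration, the same 9.5% corresponds to about 5.0% or 2.0% per year, depending on a duration that the report would not show.

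This rests on reading SAP 9.2.8 as worded and, for the figures, on a constant hazard with assumed durations and event count. The CRFs and the T-GENVIH-002 documents are not available, so whether the fields exist is unknown. The omission does not bias the proportion itself. It is a nearly free improvement to a descriptive study.

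**What to change.** 1. In SAP 9.2.5, replace the present entry with an import from T-GENVIH-002 of index-surgery date, approach (laparoscopic or robotic) and matrix configuration, linked by the T-GENVIH-002 subject number.
2. Beside the primary proportion in SAP 9.3.1, report follow-up from index surgery to Visit 1 (median and range) for all analysed subjects.
3. In SAP 9.2.8, name the index-surgery date as the time origin. Including all analysed subjects, with those free of recurrence censored at Visit 1, would follow naturally.
4. Use the imported approach for SAP 9.3.4, and the imported approach and matrix type for SAP 10.
5. Reconcile SAP 9.2.5 with 9.2.9 on index-surgery data. Reconcile SAP 10 with Protocol 10.4.8, whose wording can be read as the matrix used at reoperation; SAP 10 carries no such qualifier.

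If T-GENVIH-002 did not record these fields, remove the outputs that depend on them and state that follow-up time is unavailable.

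The cost is one linkage field if it is not already kept, one data merge and one short table. No further patient contact is needed.

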7.2 Reporting of Safety Information

7.2.1 Non-Reportable Event

Adverse Events not related to the primary hernia repair procedure will not be required to be reported by the investigator in this study.

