7.3 Reporting Requirements

7.3.1 Reporting of AEs and SAEs

The investigator will determine if there has been a potentially device or procedure related adverse event or potentially device or procedure related serious adverse event. All potentially device or procedure related adverse events and potentially device or procedure related serious adverse events must be reported on the “Adverse Event” form.

Potentially device or procedure related adverse events and potentially device or procedure related serious adverse events will be evaluated and differentiated by:

- Seriousness of the event;
- Causality of the event (in relation to the device or procedure);

- Severity of the event.

All potentially device or procedure related AEs and potentially device or procedure related SAEs must be collected for all enrolled subjects starting from the time of enrollment through the last Follow-up. Each AE must be described as follows:

AE Term: A medically defined diagnosis/symptom. Use the highest level of evidence available.

Level 1: Diagnosis (highest level)

Level 2: Symptoms

Level 3: Signs (lower level)

AE Description: Explain the circumstance of becoming aware of the event, how the subject explained the circumstances surrounding the onset of the event, the underlying cause (the diagnosis), coexisting disease, or other condition or complaint involving the event.

AE Duration: Document by entering the date of onset (start date) and date of resolution (stop date).

AE Causality: Document causal relationship between event and the investigational product and Study Procedure (causally related, possible, probably, not related).

AE Seriousness: Document as serious or not serious.

AE Severity: Document as mild (transient and easily tolerated by the subject), moderate (discomfort and interrupts normal activities), or severe (incapacitating with inability to work or do usual activity).

Action(s) Taken and/or Treatment(s): Document as none, medication, hospitalization, surgical, and/or other. Any prescribed medication should be noted in the subject's medical records and transcribed onto the AE and Concomitant Medications CRFs. If a surgical or invasive procedure is required for an AE, document the procedure on the Invasive Procedure Log.

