10.4.5 Safety Analyses

All AEs will be coded using the Medical Dictionary for Regulatory Activities (MedDRA) and presented in by-subject listings. The number and percent of subjects experiencing any AE, any related AE, and discontinuations due to an AE will be tabulated. Treatment-emergent AEs will be tabulated (frequencies and percentages) by Preferred Term (PT) within System Organ Class (SOC). If a subject experiences more than one occurrence of the same AE, and these differ in severity and/or causality, the AE will be tabulated according to the greatest severity and nearest relationship to the device. Deaths and SAEs will be listed should they occur.

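### SAP 9.3.4 confines MedDRA coding, the by-type frequency table and the withdrawal and serious-event listings to device effects, where Protocol 10.4.5 covers all AEs and SAEs

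*SAP*

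**What the plan says.** Protocol 10.4.5 (Safety Analyses) is written for AEs as a whole. On coding and listing: "All AEs will be coded using the Medical Dictionary for Regulatory Activities (MedDRA) and presented in by-subject listings". It asks for a summary line, "The number and percent of subjects experiencing any AE, any related AE", together with discontinuations caused by an AE. It also asks for a table of treatment-emergent AEs by Preferred Term (PT) within System Organ Class (SOC). On serious events: "Deaths and SAEs will be listed should they occur".

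SAP 9.3.4 (Analysis of Adverse Events) words the same outputs for adverse device effects (ADEs) and their serious form (SADEs). MedDRA coding is stated for adverse device events. The table by type reads: "A summary of the frequency count and percentage of subjects reporting each ADE category will be produced for all reported ADEs and SADEs". Withdrawals are listed when due to an ADE. On serious events: "Deaths and SADEs will be listed should they occur".

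What is collected is wider than device effects. Protocol 7.3.1 states: "All potentially device or procedure related adverse events and potentially device or procedure related serious adverse events must be reported".

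**The concern.** Events attributed to the operation but not to the matrix are collected and fall outside the ADE definition. They are the group that the SAP's narrower wording leaves out. Protocol section 10 defers detailed methods to the SAP, and the SAP says that it is based on protocol version 1.0, so a programmer would build the SAP's tables. The SAP gives no reason for narrowing them.

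At stake is whether the report gives coded frequencies by event type, and a separate serious-event listing, for everything collected. Capturing longer-term complications is the study's stated safety objective.

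**Working it through.** No figure in the plan is in dispute. The sample size of about 21 is stated not to rest on hypothesis testing, so there is nothing to reproduce. The check is a comparison of the two texts.

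**Step 1: the four outputs side by side.**

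| Output | Protocol 10.4.5 | SAP 9.3.4 |
|---|---|---|
| MedDRA coding | All AEs | Adverse device events |
| Frequency by type | Treatment-emergent AEs, PT within SOC | ADE categories, for ADEs and SADEs |
| Withdrawals | Number and percent discontinuing because of an AE | Listing of those due to ADEs |
| Serious events | Deaths and SAEs | Deaths and SADEs |

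All four are narrower in the SAP. No PT-within-SOC table is specified anywhere in the SAP.

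**Step 2: who falls in the gap.** Protocol 7.2.3 asks the sponsor and investigator to separate device-related from procedure-related events, while allowing both to apply. The SAP's AE listing has a column for each. The gap is the set of events marked related to the procedure and not related to the device.

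**Step 3: where those events still appear.**
- SAP 9.3.4, AE listing: event term, attribution to device and to procedure, and a seriousness (SAE) column.
- SAP 9.3.4, AE and SAE incidence table: patients counted by severity and by attribution, but not by type of event.
- SAP 9.3.4, mapping of AE verbatim text to group terms and body systems: this refers to AEs and so implies some grouping, but it reports a correspondence and no frequencies are specified.
- SAP 9.2.9: a summary of all complications, AEs included, with by-subject listings. No coding or term-level layout is given.
- SAP 9.3.2: SSO, SSOPI, SSI, self-reported recurrence and reoperation as proportions of subjects, with no filter on attribution.

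**Step 4: what is left uncovered.** Seroma, abscess, dehiscence, hematoma, wound necrosis, ileus, fistula and delayed wound healing are SSO components and reach the report through SAP 9.3.2. Protocol 7.2.4 also foresees pain, adhesions, chronic inflammation and injury to the bowel or bladder, none of which is a listed SSO. If judged procedure-related only, these have no specified coded frequency by term, and serious ones have no dedicated listing.

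**Step 5: size.** Let k be the number of subjects with a given event that is procedure-related only. Taking 21 as the denominator, the by-type table understates that event by k/21. One subject is 1/21 = 4.8 percentage points. The documents give no value for k, and it may be zero.

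**The case against.** The strongest reply is that nothing collected is hidden. With about 21 subjects, the AE listing shows each event with its term, attribution and seriousness, and the incidence table counts patients with AEs and SAEs whatever the attribution. The complications named in the safety objective are reported again under the SSO endpoint. SAP 9.1 also promises separate tables, listings and graphs, which could supply the missing layout.

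The gap may also be empty. Protocol 7.2.3 opens by treating use of the device as including the surgical procedure, and it sends unassessable cases to the category of possible relationship. On that reading most surgical complications would count as ADEs.

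Most of this stands, and it limits the point. A reader might infer from the ADE wording that the SAP lists only device effects, or that seroma, dehiscence, hematoma, ileus and fistula go unreported. The AE listing and SAP 9.3.2 rule out both. SAP 9.3.2 does not say whether SSOs are shown by component or only overall, but it does not drop procedure-only events.

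The reply does not remove the mismatch itself. A listing is not a frequency table, the incidence table carries no event type, and shells that follow the SAP text would inherit its scope. The ambiguity over attribution favours the protocol's version, because an all-AE table does not depend on how that ambiguity is resolved.

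**Conclusion.** The point holds as a specific inconsistency between the two documents. Four outputs that Protocol 10.4.5 sets for AEs and SAEs are confined in SAP 9.3.4 to ADEs and SADEs. The consequence is lost coding, lost term-level tabulation and no dedicated SAE listing for procedure-only events. The events themselves are not lost. The clearest effect is on non-SSO events such as pain, adhesions or organ injury.

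The size is unknown: 4.8 percentage points per affected subject if 21 enrol, times a count that the documents do not give. This assumes that investigators do mark some events as procedure-related only, and that the tables follow the SAP wording.

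Two further inferences are not supported. A reader might conclude that the whole safety report would look cleaner than the data; that can apply only to the by-type table, because the incidence table and AE listing include all collected events. A reader might also conclude that the protocol's any-AE row merely repeats the any-related-AE row, since Protocol 7.2.1 says "Adverse Events not related to the primary hernia repair procedure will not be required to be reported". But Protocol 7.3.1 collects potentially related events and then grades each for causality, with not related as an option, and 7.2.1 waives a requirement without barring such reports. The two rows can differ. If related is read there as device-related, the any-AE row is the one that carries procedure-only events.

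**What to change.** In SAP 9.3.4:
- State MedDRA coding for all collected AEs.
- Replace the ADE category table with treatment-emergent AEs by PT within SOC, and show ADEs and SADEs as a subset of it.
- Cover withdrawals due to any AE, with the count that the protocol asks for, and flag those due to ADEs.
- List deaths and all SAEs, and flag the SADEs.

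If the sponsor does intend the narrower scope, the SAP should say so and give the reason.

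Keep both the any-AE and any-related-AE rows. At most, add a footnote that only AEs potentially related to the device or procedure were required to be reported, so that the first row is not read as total AE incidence.

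The cost is a wording change in one SAP section, the matching table layouts, and coding of whatever further terms arise in about 21 subjects. No new data collection is needed.
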